- Comparative diagnostic performance of ultrafiltration tests (pooled and separate) versus pre-test postural maneuver, and between tests (15 vs. 30 minutes).
- ROC AUC values compared using DeLong's method.
- Hemodynamic variables measured by cardiac output monitoring (CVP, HR, MAP, pulse pressure, EVLW, PVPI, GEDVi), analyzed as absolute values and changes from baseline, correlated with cardiac index variation.
- Incidence of hemodynamic instability (tachycardia, hypotension, decreased cardiac index, mottling) within 8 hours after the ultrafiltration test.

Target Population

Adult ICU patients (under mechanical ventilation and sedation) with acute kidney injury (KDIGO stage 3) requiring continuous renal replacement therapy initiated within the past 14 days.

Sample Size

N = 20 evaluable patients, each undergoing 2 tests → total of 40 rapid ultrafiltration challenges.

Study Duration

- Inclusion period: 18 months
- Maximum participation per patient: 72 hours
- Total study duration: 18 months + 3 days

Expected Outcomes

The current reference dynamic test (passive leg raise or Trendelenburg) remains imperfect in assessing tolerance to fluid removal during CRRT, with sensitivity <80%. The UF challenge may prove more sensitive, particularly in patients at the borderline between the ascending and plateau phases of the Frank-Starling curve. This simple, dynamic, low-cost test could help clinicians individualize ultrafiltration prescriptions, avoid deleterious hypotension, and rapidly integrate into clinical practice. Currently, no specific dynamic test exists to evaluate the safety and efficacy of fluid removal in this population.

GENERAL INFORMATION

Title: Diagnostic performance of a rapid ultrafiltration test to assess preload dependence in critically ill patients treated with continuous renal replacement therapy.

Project Identifiers and Update History

- Sponsor Code: 69HCL21_1250
- ClinicalTrials.gov registration number: NCT05214729
- CPP Sud-Est VI favorable opinion date: XX/XX/XXXX

Version History

Version	Date	Reason for Update
1	02/11/2021	Initial draft
2	16/03/2022	Comments from CPP

Sponsor

Identity: Hospices Civils de Lyon

[name]

[name] [name]

Signature of the protocol on behalf of the Sponsor:

[name], Director of Health Research

Hospices Civils de Lyon, Health Research Directorate,

Administrative Headquarters,

[name],

[name],

[name]

[contact]

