Currently, the most reliable tool for diagnosing preload dependence is a dynamic test: passive leg raise (supine) or Trendelenburg (prone) with continuous cardiac output monitoring. A $\geq 10\%$ increase in cardiac output indicates preload dependence. Studies, including work by our team, confirm sensitivity and specificity $>85\%$. This test performs well to identify patient who are preload-dependent, and who are consequently at higher risk of preload-dependent hypotension. Yet, in preload-independent patients (i.e. those with a negative passive leg raising test, no validated predictive test exists for ultrafiltration-related hypotension in relation with their switch to a preload-dependent status.

Research Hypothesis

A 250 mL rapid ultrafiltration challenge (15 or 30 minutes) may help identify preload-independent patients at risk of becoming preload dependent during CRRT

Justification of Methodological Choices

- Sequential crossover design: each patient serves as their own control, limiting variability.
- Randomization of challenge order prevents bias.
- 250 mL volume chosen as it mimics passive leg raise (~300 mL).
- Two rates (15 vs. 30 minutes) tested to assess the effect of ultrafiltration kinetics and plasma refilling.

The PiCCO® Monitoring Device

The device combines transpulmonary thermodilution and pulse contour analysis for continuous cardiac output and displays advanced hemodynamic parameters (extravascular lung water, pulmonary vascular permeability index, global end-diastolic volume index).

Benefit/Risk Assessment

- Benefit: collective, through validation of a new predictive test.
- Risk: minimal, transient hemodynamic instability possible
- No additional invasive procedures required.

Expected Outcomes

A UF challenge may have higher diagnostic performance than the passive leg raising test to identify patients at the transition between preload independence and dependence. It is simple, dynamic, inexpensive, and potentially useful in guiding ultrafiltration in CRRT patients.

RESEARCH OBJECTIVES

Primary Objective

To evaluate the diagnostic performance of a rapid ultrafiltration challenge (250 mL over 15 or 30 minutes) in detecting preload dependence in preload independent critically ill patients treated with continuous renal replacement therapy.

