- Each patient undergoes 2 ultrafiltration challenges (15- and 30-minute, in randomized order)
- Total: 40 evaluable challenges

Randomization

- Randomized order determined by sealed envelope method
- Each patient serves as their own control

Blinding

- Not feasible given the study design

Co-interventions

Recommendation for not changing any of the following parameters, prescription or settings during the trial's interventions:

- Sedation
- Mechanical ventilation
- Vasopressor and inotrope support
- Fluid bolus therapy or transfusion

Study Procedures

1. Baseline data collection (demographics, clinical scores, renal data, hemodynamics)

2. Calibration of the monitoring device and pre-test postural maneuver (PLR or Trendelenburg) during 1 minute with collection of the relative change in continuous cardiac index
3. Ultrafiltration challenge: 250 mL over 15 or 30 minutes (randomized), by setting a UF flow of 1000 ml/h or 500 ml/h, respectively
4. Re-calibration of the monitoring device and post-test postural maneuver (reference standard, PLR or Trendelenburg) during 1 minute with collection of the relative change in continuous cardiac index
5. Repeat sequence for second challenge after a wash-out period of 24h (cross-over design)
6. Follow-up: monitoring for 8 hours post-test for instability

Data Collected

- Demographics: age, sex, weight, height
- Clinical: history, reason for ICU admission, severity scores (SAPS II, SOFA)
- Renal: CRRT indication and parameters
- Hemodynamics: CI, CVP, HR, MAP, PP, EVLW, PVPI, GEDVi (before/after each step), vasopressor dosage
- Ventilatory settings: VT, PEEP, FiO₂, arterial blood gas results
- Results of the pre and post-test postural maneuvers
- Any severe and non-severe adverse events

ENDPOINTS / EVALUATION CRITERIA

Primary Endpoint

The diagnostic performance of the rapid ultrafiltration challenge (pooled 15- and 30-minute tests).

- Performance assessed by the area under the ROC curve (AUC) of cardiac index variation.
- Reference: continuous cardiac index relative variation induced by the post-test postural maneuver performed after the challenge.

Secondary Endpoints

1. Respective diagnostic performance of the 15-minute and 30-minute challenges (ROC AUC).
2. Determination of the optimal threshold of cardiac index variation (Youden index) with sensitivity, specificity, PPV, and NPV.
3. Comparative performance of challenges (pooled and separate) versus the pre-test postural maneuver.

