4. Comparison of diagnostic performance between the 15-minute and 30-minute challenges ROC AUCs compared using DeLong's test.
5. Analysis of additional hemodynamic parameters: CVP, HR, MAP, Pulse pressure, EVLW, PVPI and GEDVi (absolute values and relative changes, correlated with cardiac index variation).

6. Incidence of hemodynamic instability within 8 hours post-test (tachycardia, hypotension, decreased CI, mottling).

Study duration

- Inclusion period: 18 months
- Maximum participation per patient: 72 hours
- Total study duration: 18 months + 3 days

Sample size

- 20 patients planned.
- Each undergoes 2 ultrafiltration challenges (15- and 30-minute, randomized).
- Total: 40 evaluable ultrafiltration challenges.

The sample size was chosen pragmatically, consistent with the pilot/exploratory nature of the study.

STUDY PROCEDURES AND CONDUCT

Overall Study Flow

1. Screening and Inclusion
 - Verify inclusion and exclusion criteria.
 - Provide information to patient or legally authorized representative; obtain consent in compliance with French law.
2. Baseline Assessment
 - Collect demographics and clinical data (age, sex, weight, height, SAPS II, SOFA, reason for ICU admission, history).
 - Record renal data (CRRT indication and parameters, time since CRRT initiation).
 - Baseline hemodynamic measurements: CI, CVP, HR, MAP, PP, EVLW, PVPI, GEDVi, vasopressor dosage
 - Mechanical ventilation settings
3. Randomization
 - Determine challenge sequence (15 vs 30 minutes) using sealed envelopes.
4. Pre-test postural maneuver
 - Passive leg raise (supine) or Trendelenburg (prone).
 - Record hemodynamic parameters before and during maneuver.
5. Ultrafiltration Challenge
 - Remove 250 mL with UF over 15 or 30 minutes.
 - Monitor CI and hemodynamic parameters continuously.
 - Record parameters at the end of challenge.
6. Post-test Postural Maneuver (Reference)
 - Repeat maneuver (PLR or Trendelenburg).
 - Record hemodynamic parameters before and during maneuver.
7. Follow-up
 - Any hemodynamic instability episodes occurring over the following 8h

8. Second Ultrafiltration Challenge

- After a 24h wash-out period, repeat procedure with the alternate duration (30 or 15 minutes).
- Same sequence: pre-test maneuver → challenge → post-test maneuver.

9. Follow-up

- Monitor for 8 hours post-challenges.
- Record any hemodynamic instability.

Data Management

- Data recorded in a secure **electronic case report form (eCRF)**.

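### Secondary endpoint 3 scores the UF challenge and the pre-test postural maneuver against a repeat of that same maneuver, so an AUC difference measures agreement with the maneuver, not accuracy for preload dependence

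*Combined protocol and SAP*

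**What the plan says.** Endpoints / Evaluation Criteria, Secondary Endpoints item 3, sets up a head-to-head: "Comparative performance of challenges (pooled and separate) versus the pre-test postural maneuver". The Primary Endpoint in the same section defines the reference: "Reference: continuous cardiac index relative variation induced by the post-test postural maneuver performed after the challenge". The Statistical Analysis section names no other truth for any AUC.

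Overall Study Flow shows that reference and comparator are one procedure done twice. Step 6 reads "Repeat maneuver (PLR or Trendelenburg", and step 8 gives the order: "Same sequence: pre-test maneuver → challenge → post-test maneuver". The Summary, Secondary Endpoints, adds "ROC AUC values compared using DeLong's method". Item 3 of the Secondary Analyses also names DeLong's test, although its wording mixes in the 15- versus 30-minute comparison.

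The hoped-for conclusion is about accuracy. The Summary, Expected Outcomes, says that the current dynamic test "remains imperfect in assessing tolerance to fluid removal during CRRT, with sensitivity <80%. The UF challenge may prove more sensitive". The later Expected Outcomes paragraph, just before Research Objectives, says: "A UF challenge may have higher diagnostic performance than the passive leg raising test to identify patients at the transition between preload independence and dependence". No correction for an imperfect reference and no caution about interpreting this comparison is given.

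**The concern.** The question posed is which test better detects preload dependence. The planned comparison answers a different one: which test agrees better with a second postural maneuver, in the same patient with the same monitor, on the other side of one 15- or 30-minute challenge.

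Suppose something about a patient makes the maneuver misleading both times. The error then appears in the pre-test result and in the reference, and counts as agreement. A UF result that is right in that patient counts as wrong. With such repeated error the null of equal AUC is no longer a null of equal accuracy. At stake is the one planned comparison that could seem to support the statements in the two Expected Outcomes paragraphs, and a real advantage of the UF challenge could be hidden or inverted.

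**Working it through.** **Inputs from the documents.** 20 patients × 2 challenges = 40, which reproduces the stated total. Two-sided 0.05. A 10% rise as the cut-off (background text only). Maneuver accuracy is given in two ways: sensitivity below 80% for tolerance to fluid removal (Summary), and sensitivity and specificity above 85% for preload dependence (background). No expected AUC, AUC difference or repeatability of the maneuver is given, so everything else below is assumed.

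**Model A.** True response S after the challenge has mean 8% and SD 6%. Each maneuver reads S plus error of SD σ, of which a share ρ of the variance is common to both maneuvers. UF reads S plus error of the same SD, so both tests have equal AUC against the true state. With s the share of error variance that UF has in common with the reference, the correlations with the reference are:

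- pre-test maneuver: (36 + ρσ²) / (36 + σ²)
- UF challenge: (36 + sσ²) / (36 + σ²)

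Only ρ versus s separates the two. With σ = 4, the reference has about 79% sensitivity and 84% specificity, and both tests have a true AUC of 0.90. With s = 0, the UF correlation is 36/52 = 0.692 throughout.

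| ρ | Correlation, pre-test maneuver | AUC vs reference, maneuver | AUC vs reference, UF | Gap | DeLong favours maneuver |
|---|---|---|---|---|---|
| 0 | 36/52 = 0.692 | 0.829 | 0.828 | 0.00 | 2% |
| 0.25 | 40/52 = 0.769 | 0.868 | 0.829 | +0.04 | 8% |
| 0.5 | 44/52 = 0.846 | 0.910 | 0.827 | +0.08 | 21% |
| 0.75 | 48/52 = 0.923 | 0.953 | 0.827 | +0.13 | 47% |

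The last column should be near 2.5%. It treats the 40 challenges as independent, although there are two per patient, so it is approximate.

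*Other reference accuracies, ρ = 0.5.* At 84%/89% the gap is 0.950 − 0.903 = +0.05. At 72%/78% it is 0.858 − 0.732 = +0.13.

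*Error-free UF test.* Its correlation with the reference is 6/√52 = 0.832 and its AUC reads 0.90, although its true AUC is 1.00. The maneuver overtakes it once (36 + 16ρ)/52 exceeds 0.832, that is ρ > (0.832 × 52 − 36)/16 = 0.45. At ρ = 0.5 the maneuver reads 0.91.

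*Error shared by UF and the reference.* With ρ = 0, s = 0.25 and 0.5 give gaps of −0.04 and −0.08. With s = ρ the gap is zero.

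**Model B, a second parameterisation.** Preload reserve is standardised, 30% are preload dependent, and reserve changes between the maneuvers with SD 0.3 or 0.5. UF is tuned to the same true AUC as the pre-test maneuver.

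- Maneuver sensitivity 0.73–0.81 and specificity 0.88–0.92: gap 0.05–0.08 when half of the error variance repeats, 0.08–0.14 when 80% does.
- Accuracy near the background figure of above 85%: gap about 0.03 and 0.04–0.05 respectively.
- No repeated error: DeLong rejects in 4–5% of runs, as it should.

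**Entry exclusion.** Keeping only patients with a pre-test response below the cut-off compresses the range of the pre-test reading. In Model A with a state change between the maneuvers, the true AUCs become 0.78 (maneuver) and 0.83 (UF). The gap against the reference (maneuver minus UF) is −0.03, 0.00, +0.04 and +0.08 at ρ = 0, 0.25, 0.5 and 0.75, so from ρ = 0.5 the ranking is the reverse of the truth. In Model B, with half of the error repeating and UF noise unchanged, the gap is about −0.01 to +0.06.

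**The case against.** The strongest reply is that the direction depends on a quantity the documents never give. With independent maneuver errors there is no bias. The exclusion list removes some causes of a repeatedly misleading leg raise (amputation, vena cava obstruction, abdominal compartment syndrome), and the monitor is re-calibrated before the second maneuver. For preload dependence itself the protocol claims accuracy above 85%, which roughly halves the gap. Patients known to be preload dependent are not enrolled, which pulls against the maneuver. All of this stands, and it rules out stating a direction as fact. It does not restore the comparison: each of these features moves the AUC difference without any change in true accuracy, or leaves it at odds with the true ranking.

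A reader might infer that the plan always favours the maneuver, or that the UF challenge can never come out ahead. The documents do not support either. The comparator is the pre-test maneuver, and against the post-test reference a better UF test can exceed it when little error repeats. That UF cannot be shown more sensitive than the maneuver that defines the truth is correct, but it is true of any reference standard.

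It is also fair that the protocol regards the maneuver as the best available tool, that both Expected Outcomes paragraphs say only that UF may do better, and that this is a secondary comparison in a pragmatically sized pilot. The primary AUC does not involve the pre-test maneuver, although it rests on the same reference. These points limit the weight of the concern, not its logic.

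**Conclusion.** The point holds in conditional form. That the comparator and the truth are the same maneuver follows from the text alone, so the AUC comparison is one of agreement with a repeat maneuver. If the maneuvers share error more than UF and the reference do, it favours the maneuver at equal true accuracy: about 0.03 to 0.08 AUC without entry restriction when half of the error variance repeats, and nothing when none does. This range is illustrative and not a bound, since a less accurate reference (72%/78%) gave 0.13. Repeated error is plausible, but its share is an assumption.

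The entry exclusion can shrink or reverse the gap. So can an end-of-challenge cardiac index reading that serves both the UF change and the reference; the documents do not say whether one does. Size and direction therefore cannot be fixed from the documents, and a difference in either direction, significant or not, should not be read as a difference in accuracy. The plan should be changed, but this does not affect the definition of the primary analysis.

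**What to change.** 1. Keep the comparison against the post-test maneuver, but label and report it as agreement with a repeat maneuver. Do not use it to conclude that the UF challenge is more sensitive than, or performs better than, the postural maneuver. State which cardiac index readings feed the UF change and which feed the reference. The cost is wording only.

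2. Add an exploratory paired comparison of the UF cardiac index change and the pre-test maneuver change as predictors of instability in the 8 hours after each challenge, using hypotension, tachycardia and mottling. Leave out decreased cardiac index, because it shares the measurement on which both tests rest. Give the AUC difference with a 95% confidence interval, resampling patients so that the two challenges per patient stay together. Report it beside the outcome in secondary objective 6, instability with preload dependence. At present item 5 of the Secondary Analyses only describes incidence. If preload dependence in that outcome is judged by a postural maneuver, part of the problem returns, which is why the clinical components are needed as well.

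The data are already collected, so the cost is one analysis. There are limits. Events may be few and the interval wide. Clinical instability is not specific to preload dependence, as the Summary's background itself notes. The study is open-label, so test results can influence treatment and through it the outcome. The comparison should be presented as exploratory.

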STATISTICAL ANALYSIS

General Principles

- Analyses performed using R software (latest version available).
- Two-sided significance level set at 0.05.
- 95% confidence intervals reported.
- Analyses conducted on the intention-to-treat and per-protocol population (patients with at least one evaluable ultrafiltration challenge).

Primary Analysis

- The primary endpoint is the diagnostic performance of the ultrafiltration challenge (15- and 30-minute tests pooled).
- Performance assessed by calculating the area under the ROC curve (AUC) of cardiac index variation compared with the post-test postural maneuver.
- AUC values will be reported with 95% confidence intervals.

Secondary Analyses

1. Diagnostic performance of the 15-minute and 30-minute ultrafiltration challenge alone (ROC AUC).
2. Determination of the optimal threshold of cardiac index variation (Youden index) defining preload dependence, with sensitivity, specificity, PPV, and NPV.
3. Comparative diagnostic performance of ultrafiltration challenges (pooled and separate) versus the pre-test postural maneuver, compared using the

respective ROC AUCs of 15-minute and 30-minute challenges using DeLong's test.

4. Analysis of additional hemodynamic parameters (CVP, HR, MAP, PP, EVLW, PVPI, GEDVi) in absolute values and relative changes from baseline, correlated with cardiac index variation using Pearson or Spearman correlation.
5. Description of the incidence of hemodynamic instability within 8 hours post-test, expressed as proportions with 95% confidence intervals.

Handling of Missing Data

- Missing data will not be imputed.
- Analyses will be based on available data.
- The extent and reasons for missing data will be described.

Interim Analysis

No interim analysis is planned.

QUALITY ASSURANCE, ETHICS, AND DATA MANAGEMENT

Regulatory and Ethical Aspects

- The study will be conducted in compliance with the Declaration of Helsinki (2013 version) and the principles of Good Clinical Practice (ICH E6 R2).
- The protocol, patient information, and consent form have been submitted to and approved by the CPP Sud-Est VI (Comité de Protection des Personnes).
- The study has been declared to the CNIL (Commission Nationale de l'Informatique et des Libertés) in accordance with French law and the General Data Protection Regulation (GDPR, EU 2016/679).

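### DeLong's test is named for the 15- versus 30-minute comparison without a form that fits the crossover: the paired form does not apply, and the unpaired form discards the within-patient gain

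*Combined protocol and SAP*

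**What the plan says.** The Secondary Endpoints list in the endpoints section has as item 4: "Comparison of diagnostic performance between the 15-minute and 30-minute challenges ROC AUCs compared using" DeLong's test. The Summary says of the comparisons as a group: "ROC AUC values compared using DeLong's method". Item 3 of Secondary Analyses, in the Statistical Analysis section, starts with ultrafiltration against the pre-test manoeuvre and ends with the "respective ROC AUCs of 15-minute and 30-minute challenges using DeLong's test". None of these places says whether the paired or the unpaired form is meant. None mentions a variance clustered by patient or resampling by patient.

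On the design, under Number of Patients: "Each patient undergoes 2 ultrafiltration challenges (15- and 30-minute, in randomized order". Step 4 of Study Procedures gives each challenge its own reference: "Re-calibration of the monitoring device and post-test postural maneuver (reference standard, PLR or Trendelenburg) during 1 minute". Step 5 repeats the sequence after a 24 h wash-out. The reason given for the crossover, under Justification of Methodological Choices, is that "each patient serves as their own control, limiting variability".

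**The concern.** DeLong's test comes in two forms, and neither matches these data.

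- **Paired.** It compares two markers measured on the same units against one common true status. Here a patient has two reference results on different days and may be positive at one challenge and negative at the other. The test would run only if one day's reference were imposed on both challenges, which biases the comparison.
- **Unpaired.** It lets each curve keep its own reference but assumes that the two samples are independent. The same patients are in both, so it leaves out the covariance that the crossover was chosen to exploit.

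At stake are the precision of the 15- versus 30-minute comparison and, because the form is left open, the chance that an analyst forces the paired form. The AUC for each duration taken alone is not affected.

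**Working it through.** **Inputs from the documents.** 20 patients; two challenges each (20 × 2 = 40); one post-test reference per challenge; 24 h wash-out; two-sided 0.05. The plan gives no power, target AUC or prevalence, so there is no stated figure to reproduce.

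**Assumptions not in the documents.** 30% of references positive (6 of 20), both true AUCs 0.75, and a common within-patient correlation between the two challenges (ICC) of 0.3 to 0.9, applied to the marker and to the latent reference.

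**Formulas.** For challenge k with m positives and n negatives, give each patient p a component D(p,k). This is (placement value − AUC) divided by √(m(m−1)) if p is positive at that challenge, or by √(n(n−1)) if negative.

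- Unpaired variance of the difference: Σ D(p,15)² + Σ D(p,30)²
- Patient-clustered variance: Σ [D(p,15) − D(p,30)]², which is the unpaired variance minus 2 Σ D(p,15)·D(p,30)

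The cross-product is the crossover's gain. It needs no common reference, because each component uses that challenge's own status.

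**Step 1: how often the reference changes.** At ICC 0.3, 0.5, 0.7 and 0.9, about 34%, 29%, 22% and 12% of patients have different results at the two challenges. All 20 pairs agree in at most about 7% of simulated trials. The paired form's condition will almost never be met by luck.

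**Step 2: unpaired DeLong, no true difference.**

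| ICC | Mean unpaired SE | True SD of difference | Ratio | Type I error |
|---|---|---|---|---|
| 0.3 | 0.179 | 0.175 | 1.02 | 5.3% |
| 0.5 | 0.177 | 0.165 | 1.07 | 4.2% |
| 0.7 | 0.178 | 0.146 | 1.22 | 2.3% |
| 0.9 | 0.177 | 0.113 | 1.57 | 0.5% |

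In terms of the 95% CI, at ICC 0.9 the unpaired half-width is 1.96 × 0.177 = 0.35, where 1.96 × 0.113 = 0.22 would do. At ICC 0.3 it is 1.96 × 0.179 = 0.35 against 1.96 × 0.175 = 0.34.

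The correlation between the two AUC estimates implied by the table, 1 − (SD/SE)², is 0.04, 0.13, 0.33 and 0.59. It stays well below the ICC, which is why the loss is negligible at low ICC.

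**Step 3: patient-clustered variance.** In the same settings it tracks the true SD, with type I error of about 3% to 7%. Power for an assumed AUC of 0.90 against 0.70 rises from 14–23% (unpaired) to 24–40%.

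**Step 4: other assumed values.** With 40% positive and both AUCs 0.75, unpaired type I error is 0.046 to 0.059 when the correlation is nil or weak. It falls to 0.009 at a reference correlation of 0.9 and a marker correlation of 0.8 (SE 0.170 against SD 0.113). Clustered type I error is 0.034 to 0.066. Power for 0.90 against 0.70 is 0.18–0.27 unpaired and 0.27–0.37 clustered.

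**Step 5: forcing the paired form.** With the values of step 4, imposing one day's reference on both challenges gives a spurious AUC difference of about 0.07 to 0.25 and type I error of 0.08 to 0.59. The upper limit can be checked by hand. If the two days are unrelated, 2 × 0.4 × 0.6 = 48% of patients change status, the other day's marker has AUC 0.50 against the imposed reference, and 0.75 − 0.50 = 0.25.

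**Step 6: the two comparisons.** Secondary Objectives 3 and 4 list ultrafiltration against the pre-test manoeuvre and 15 against 30 minutes as separate aims. Endpoints 3 and 4 do the same. Item 3 of Secondary Analyses runs them into one sentence. Within one duration, the challenge and its pre-test manoeuvre share one post-test reference, so paired DeLong is suitable there.

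**The case against.** A reader might infer that DeLong's test cannot validly be used here, or that it will produce false positives. The documents do not support that. They do not ask for the paired form. The unpaired form can be computed with each challenge's own reference, and in every setting tried its type I error was at most about 6%, usually below 5%. Its fault is inefficiency. Negative within-patient correlation was not simulated and could reverse the direction.

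A reader might also infer from item 3 of Secondary Analyses that the comparison with the pre-test manoeuvre will not be done. That does not hold either. The comparison is listed separately in the Summary, the objectives and the endpoints, and the Summary applies DeLong's method to it. The document is also a translation whose French original prevails. The sentence needs repair; no analysis has been left out.

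Two further objections carry weight. The high rate of changed references and the large excess in SE come from opposite ends of the ICC range: about 34% of patients change status at ICC 0.3, where the SE is nearly right, and about 12% at ICC 0.9, where it is 57% too large. And a patient-level percentile bootstrap, the obvious alternative, is not clearly better at this size: its simulated type I error reached about 7% to 9% at low to moderate ICC.

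Finally, this is a secondary comparison in a pilot with a pragmatic sample size. That limits the importance of the point, but the better method costs almost nothing.

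**Conclusion.** The concern holds as a mismatch between test and design. The paired form does not apply to 15 versus 30 minutes. The unpaired form is usable but conservative: its SE is about right at ICC 0.3 and about 7%, 22% and 57% too large at 0.5, 0.7 and 0.9, with type I error of about 4%, 2% and 0.5%. The only route to inflated false positives found here is imposing one day's reference on both challenges, which the plan does not request but does not rule out.

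The design facts come straight from the documents. The sizes rest on assumed prevalence, AUC and non-negative within-patient correlation, none of which the documents give. The change should be made, but it does not touch the primary endpoint.

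**What to change.** 1. **15 versus 30 minutes.** State that the AUC difference (15 minus 30) is estimated with each challenge's own post-test reference and a patient-clustered DeLong-type variance, and is reported with its 95% CI. State that no reference result is carried from one challenge to the other. A patient with one evaluable challenge contributes to that curve only, in keeping with the rule against imputation.
2. **Sensitivity analysis.** A bootstrap that resamples whole patients, with a note that its percentile form can be somewhat anti-conservative with 20 patients.
3. **Item 3 of Secondary Analyses.** Split it to match Secondary Objectives 3 and 4: (a) ultrafiltration against the pre-test manoeuvre, both judged by the same post-test reference, with paired DeLong within each duration and a patient-clustered variance when the durations are pooled; (b) 15 against 30 minutes as in point 1.

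The cost is a few lines of SAP text and a short script, with no extra patients or data. The downside is that the clustered variance is a large-sample approximation used here with few positives (simulated type I error about 3% to 7%). The result should be presented as exploratory, with the interval rather than the p-value in front.
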